6.4 Strategies for Recruitment and Retention

Subjects will be recruited from the study center's regular pool of patients undergoing hemodialysis. Due to the number of subjects required for this study, additional advertising and/or recruitment methods should not be required.

Additionally, because each patient is expected to complete the study in approximately one month, no exceptional retention methods will be used. A payment (via check) in an amount of \$50 per visit will be provided to the subjects to cover the subjects' additional time and/or expenses at the completion of the final visit.

7 Study Intervention

7.1 Study Intervention(s) Administration

7.1.1 Study Intervention Description

The Hemotek V Needle A.V. Fistula Set is intended for temporary cannulation (non-implanted) to vascular access for extracorporeal blood treatment for hemodialysis. Please refer to device labeling for additional information. The device is intended for single use only. The device also has an integrated safety mechanism that is designed to automatically occlude the internal fluid path and trigger the hemodialysis machine to alarm and shut off if a complete dislodgement of the venous needle from the arm inadvertently occurs.

For the clinical studies, the Hemotek 15-gauge, 1 inch length, with 12 inch tubing, V Needle Sharp configuration will be used. Devices will be packaged individually, and a clamp will be used.

7.2 Preparation/Handling/Storage/Accountability

7.2.1 Acquisition and accountability

The devices will be hand-delivered to the investigative site. Product that is not immediately in use will be stored in a locked cabinet. Expired or unused product will be retrieved by the sponsor.

7.2.2 Formulation, Appearance, Packaging, and Labeling

The device will be provided with appropriate packing and labeling, including a clear indication of the expiration date of the product. The device will be provided sterile.

7.2.3 Product Storage and Stability

The storage requirements will be indicated by the device packaging and labeling. The devices are single use. The expiration date of the device will be clearly indicated on the device.

7.2.4 Preparation

Refer to the device's instruction for use for appropriate administration of the device.

7.3 Measures to Minimize Bias: Randomization and Blinding

The study is not randomized or blinded. Control sessions measuring the rates of adverse events and successful therapy sessions is included to provide a within-subject comparator to these rates for the V Needle. To minimize bias, subjects will be considered and asked to enroll in the study sequentially to the extent possible to ensure that no unconscious bias of patient selection occurs. The study will be conducted at multiple centers to ensure that outcomes are able to be generalized across different clinics.

At least two different clinicians will evaluate the device for each patient and for each needle for that patient (test and control) to minimize the bias associated with the same clinician evaluating all of the sessions for a given subject.

7.4 Study Intervention Compliance

Adherence to the study protocol will be accomplished by the direct supervision of the study clinicians and review of the clinical data by study monitors.

8 Study Intervention Discontinuation and Participant Discontinuation/Withdrawal

8.1 Discontinuation of Study Intervention

Discontinuation from one study visit does not mean discontinuation from the study, and remaining study procedures should be completed as indicated by the study protocol. If a clinically significant finding is identified (including, but not limited to changes from baseline) after enrollment, the investigator or qualified designee will determine if any change in participant management is needed. Any new clinically relevant finding will be reported as an adverse event (AE).

8.2 Participant Discontinuation/Withdrawal from the Study

Participants are free to withdraw from participation in the study at any time upon request.

A patient who is no longer active in the study, due either to patient choice or physician recommendation, will be classified as a "Withdrawal." All completed case report forms up to the point of withdrawal must be completed.

After a patient has been withdrawn from the study or after a patient has withdrawn his/her consent, for whatever reason, additional data may no longer be collected after the point of withdrawal. All open adverse events should be closed or documented as chronic. Data collected up to the point of patient withdrawal may be used for analysis. The sponsor will not actively collect any information on subjects who have been withdrawn from the study. However, all post-withdrawal adverse events of which the sponsor is notified will be recorded in the patient file.

The reason for participant discontinuation or withdrawal from the study will be recorded on the Study Completion Form (CRF).

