9.1.4 Final Study Visit

7-10 days after the last study visit, subjects will be contacted by phone or will be interviewed at their usual hemodialysis session to ensure no additional AEs have occurred.

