9.2.2 AE and Device Deficiency Documentation

All AEs will be monitored for all participants, from the time of signing consent through to the final study visit. All AEs, including SAEs, must be detailed in the source documents and reported in a timely manner to the Sponsor by completing an AE page in the CRF. Each unique event must be documented separately.

AEs can be based upon subject report, questionnaires, medical reports or other medical examinations. AEs should be documented in terms of a medical diagnosis. When this is not possible, the AE should be documented in terms of signs and/or symptoms observed by the Investigator or reported by the subject at each study visit. For each medical diagnosis or sign and/or symptoms the Investigator will provide information on dates (onset/resolution), severity, relationship to the medical device, action(s) taken and outcome.

Any AEs should be followed until the event is resolved (with or without sequelae). If an event is ongoing at the time of study completion or termination, the participant will be followed until resolution or Investigator determination that the subject's condition is stable. Documentation of stabilization must be recorded in the participant's source documents. If the Investigator learns of any SAE at any time after a participant has been discharged from the study, and he/she considers

the event reasonably related to the study device and/or study procedure, the Investigator will record the occurrence in the subject's source documents and promptly notify the Sponsor.

If adverse events occur, the first concern will be the safety of the subject. Appropriate medical intervention will be made as soon as possible. Treatment of any AEs is at the sole discretion of the Investigator and according to current good medical practice. Any medication administered for the treatment of an AE should be recorded in the CRF.

All device deficiencies, including serious incidents (a device deficiency that might have led to a SADE if a) suitable action had not been taken, b) intervention had not been made, c) if circumstances had been less fortunate), shall be documented throughout the study in the source documents and appropriately reported on a device deficiency page of the CRF.

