9.2.13 Time Period and Frequency for Event Assessment and Follow-Up

The occurrence of an adverse event (AE) or serious adverse event (SAE) may come to the attention of study personnel during study visits and interviews of a study participant presenting for medical care, or upon review by a study monitor.

All AEs including local and systemic reactions not meeting the criteria for SAEs will be captured on the appropriate case report form (CRF). Information to be collected includes event description, time of onset, clinician's assessment of severity, relationship to study product (assessed only by those with the training and authority to make a diagnosis), and time of resolution/stabilization of the event. All AEs occurring while on study must be documented appropriately regardless of relationship. All AEs will be followed to adequate resolution.

Any medical condition that is present at the time that the participant is screened will be considered as baseline and not reported as an AE. However, if the study participant's condition deteriorates at any time during the study, it will be recorded as an AE.

Changes in the severity of an AE will be documented to allow an assessment of the duration of the event at each level of severity to be performed. AEs characterized as intermittent require documentation of onset and duration of each episode.

Study clinicians will record all reportable events with start dates occurring any time after informed consent is obtained until 7 days after the last day of study participation. At each study visit, the investigator will inquire about the occurrence of AEs since the last visit. Events will be followed for outcome information until resolution or stabilization.

10 Statistical Considerations

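### Section 8.2 ends data collection for physician-recommended withdrawals who still consent, which conflicts with the adverse event follow-up rules in 9.2.2, 9.2.13 and 1.12

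*Combined protocol and SAP*

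**What the plan says.** Section 8.2 defines the class of withdrawals broadly, in the sentence that begins "A patient who is no longer active in the study, due either to patient choice or physician recommendation, will be classified as". It then treats being withdrawn and withdrawing consent alike, whatever the reason:

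- Collection stops on that date: "additional data may no longer be collected after the point of withdrawal".
- AEs not yet resolved by then get an administrative end: "All open adverse events should be closed or documented as chronic".
- For the analysis, only what was gathered before the subject left is named as usable.
- No effort is made to obtain more: "The sponsor will not actively collect any information on subjects who have been withdrawn from the study".

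One passive route is kept in 8.2: post-withdrawal AEs that the sponsor hears about go into the patient file.

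Other sections set AE duties without excepting withdrawn subjects. Section 9.2.2 has AEs monitored for every participant from consent to the final study visit and adds: "Any AEs should be followed until the event is resolved (with or without sequelae"). Section 9.2.13 also requires follow-up to resolution and sets the recording period as "any time after informed consent is obtained until 7 days after the last day of study participation". Section 1.12 records AEs for a week after the last session when no further session is planned. Section 9.1.4 describes a closing safety contact, timed at 7 to 10 days from the final visit, in these words: "subjects will be contacted by phone or will be interviewed at their usual hemodialysis session to ensure no additional AEs have occurred".

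**The concern.** Stopping collection is understandable when a subject withdraws consent to it. A physician's recommendation to leave the study is a different situation: the subject may still agree to be contacted, and may be leaving with an open AE. Section 8.2 does not separate the two, so a site holding such a subject has two sets of instructions that cannot both be followed.

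What is at stake is complete ascertainment of late events. Section 1.12 itself anticipates them, giving a hematoma in the days after a session as its example. The SADE rate is the primary safety measure (4.1), and the rates of AEs, adverse device effects and adverse procedure effects are additional measures (4.2). All of them rest on 15 to 20 subjects.

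**Working it through.** **1. The rules side by side, for a physician-recommended withdrawal with consent intact**

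| Question | Section 8.2 | Elsewhere |
|---|---|---|
| Are new AEs sought after the subject leaves? | No; passive notification only | 9.2.2: all participants, to the final visit. 9.2.13: to 7 days after participation. 1.12: one week after the last session |
| What happens to an open AE? | Closed or labelled chronic | 9.2.2 and 9.2.13: followed to resolution; 9.2.2 accepts stability if ongoing at study completion or termination |
| Is there a final safety contact? | None provided | 9.1.4: 7–10 days after the last study visit. Table 1 (1.23): 7–10 days after Visit 9 |

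The first two rows conflict. The third is a gap: Table 1 ties the contact to Visit 9, so it is not clearly defined for a subject who leaves earlier.

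**2. Direction of any bias**

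Section 10.3.2 computes events per treatment and assigns events between sessions to the device last used. Subjects who do not finish the control sessions are screen failures outside the subject count (6.3), so counted withdrawals come after the controls. Section 10.4.2 uses available data without imputation.

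Let N be the V Needle sessions completed, B the events recorded before withdrawal, A the events arising after it within the recording window, and c the fraction of A that passive routes bring into the analysis.

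- Rate with full ascertainment: (B + A) / N
- Rate under 8.2: (B + cA) / N
- Bias: −(1 − c)A / N, which is zero or negative

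The completed sessions stay in N whatever happens to A. The documents give neither A nor c, so the size cannot be computed.

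**3. Illustration for the primary safety measure**

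The plan's session count reproduces as 18 × 6 = 108. Section 10.1.1 treats 108 as allowing for 20% attrition or missed sessions around a requirement of 87 (108 × 0.80 = 86.4). Section 10.3.1 treats 108 as what remains after attrition. Both denominators are therefore shown.

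The exact 95% upper limit for k events in n sessions is the 0.975 quantile of Beta(k + 1, n − k). For k = 0 this equals 1 − 0.025^(1/n). The event counts are assumptions.

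| n | 0 SADEs: rate, upper limit | 1 SADE: rate, upper limit | Shift in upper limit |
|---|---|---|---|
| 108 | 0%, 3.36% | 0.93%, 5.05% | 5.05 − 3.36 = 1.69 points |
| 87 | 0%, 4.15% | 1.15%, 6.24% | 6.24 − 4.15 = 2.09 points |

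**4. Ceiling on the subjects affected**

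If the whole 20% allowance were withdrawals: 0.20 × 15 = 3.0, 0.20 × 18 = 3.6 and 0.20 × 20 = 4.0 subjects. This is a ceiling because the allowance in 10.1.1 also covers missed V Needle sessions, and because withdrawals include consent withdrawals and, under 8.3, subjects who cannot be reached.

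**The case against.** The best defence is that 8.2 is a specific exception to the general AE rules and that safeguards remain. Much of the defence on safeguards stands.

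- Section 8.1 keeps a subject in the study after one discontinued visit. A reader might infer that anyone taken off the V Needle loses follow-up. The documents do not support that: 8.2 reaches only subjects no longer active in the study. However, 8.1 does not say what happens when a subject permanently stops V Needle sessions.
- An AE that prompts withdrawal is already recorded, and closing it does not remove it from the count. Only later new or worsening events are exposed.
- Section 9.2.2 obliges the investigator to report related SAEs learned of at any time after discharge from the study. Subjects come from the center's regular dialysis pool (6.4), so a serious access event may well reach the site. This partly protects the SADE count. Non-serious device effects have only passive notification, and 8.2 sends those to the patient file without mentioning the CRF or the analysis.
- A reader might infer that the stopping rule in 5.3 is undermined. Its SADE trigger counts three SADEs in the study device period that require intervention, and a post-withdrawal event might not qualify.
- A reader might also infer that physician-withdrawn subjects are the likeliest to have late events, or that the chronic label would be mistaken for a seriousness criterion. No passage supports the first. On the second, 9.2.4 collects seriousness separately from event status.

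The exception reading does not settle the matter. Section 8.2 does not present itself as an exception, and 9.2.2 speaks of all participants.

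**Conclusion.** The conflict is real but narrow. It applies to a subject permanently withdrawn on a physician's recommendation who has not withdrawn consent, and it lies between 8.2 on one side and 9.2.2, 9.2.13 and 1.12 on the other. The final contact for a subject leaving before Visit 9 is undefined rather than contradicted.

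The documents show a risk of under-counting, not that under-counting will occur. Its direction is downward and its size is unknown. The shifts of 1.69 and 2.09 points assume exactly one missed SADE, and 3 to 4 of 18 subjects assumes that every lost session came from a withdrawal. Safety is summarized descriptively with exact bounds (10.3.2), so no pass or fail conclusion turns on this. It should be fixed, because following 8.2 as written leaves late device events unsought while the sessions stay in the denominator.

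**What to change.** Reconcile 8.2 with 9.2.2, 9.2.13 and 1.12 by defining two categories.

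1. **Withdrawal of consent to further contact or data collection.** Apply the no-further-collection rule and AE close-out only here, and record the outcome of an open AE as unknown at withdrawal of consent. The status list in 9.2.4 has no such entry, so one must be added.
2. **Stopping study sessions, or physician-recommended withdrawal, with consent to contact intact.** Make the existing 7–10 day safety contact, counted from the last session attended. Follow open AEs as 9.2.2 states, and enter the data in the CRF and the safety analysis.

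Align 9.1.4 and Table 1 so that the contact is defined for a subject who leaves before Visit 9. None of this alters who stops V Needle sessions, or when.

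The cost is a protocol amendment with IRB review (section 2) and a few phone calls or interviews at usual dialysis sessions, which 9.1.4 already permits. Whether the consent form needs a matching change cannot be judged from the documents available. Sample size and the primary performance analysis are unaffected.

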8.3 Lost to Follow-Up

A participant will be considered lost to follow-up if he or she fails to return for any scheduled visit and is unable to be contacted by the study site staff.

The following actions must be taken if a participant fails to return to the clinic for a required study visit:

- The site will attempt to contact the participant and reschedule the missed visit and counsel the participant on the importance of maintaining the assigned visit schedule and ascertain if the participant wishes to and/or should continue in the study.
- Before a participant is deemed lost to follow-up, the investigator or designee will make every effort to regain contact with the participant (where possible, 3 telephone calls and/or written communication). These contact attempts should be documented in the participant's medical record or study file.
- Should the participant continue to be unreachable, he or she will be considered to have withdrawn from the study with a primary reason of lost to follow-up.

9 Study Assessments and Procedures

This section describes the study assessments and procedures. Refer to Table 1 for a list of the data to be collected at each visit. Study staff will check for AEs at each visit and fill out an AE form as necessary.

9.1 Efficacy Assessments

9.1.1 Enrollment

At the enrollment visit, the informed consent document and inclusion/exclusion criteria will be assessed and entered into the Inclusion/Exclusion Case Report Form. Multiple visits to complete the screening and obtain appropriate informed consent are allowed. Demographics and medical history will be collected, as well as vital signs (height, weight, blood pressure, heart rate, respiration, and temperature).

9.1.2 Control Dialysis Sessions

The assessment of the ability to successfully complete the session will be determined by the clinician and recorded on the Therapy Assessment Case Report Form (CRF). The actual treatment time will also be recorded. Adverse events will be recorded on an Adverse Event Case Report Form. Photos of the cannulation may be taken.

Additional performance measures include the following:

- Machine alarm rate (blood alarms only) during hemodialysis therapy, including false alarms and relationship of alarm to venous needle
- Changes to blood flow rate setting during therapy sessions and relationship to venous needle
- Venous, transmembrane, and/or arterial pressure measurements
- Clinician survey, evaluating the following items:
 - use of the device according to the instructions for use (IFU)
 - ability to properly cannulate
 - ability to objectively see flashback
- Achieved treatment time
- Achieved blood flow rate
- Ability to cannulate fistula
- Episodes of partial or complete needle dislodgment

In the event that the venous needle becomes 1) completely dislodged, or 2) partially dislodged and the venous pressure increases by more than 40 mm Hg indicating some disruption of the fluid flow, the event should be recorded on the therapy assessment and AE CRFs and appropriate laboratory tests (including CBC, plasma hemoglobin concentration, serum electrolytes) shall be obtained.

Patients shall be monitored for symptoms of hemolysis; if hemolysis is suspected, an AE form should be completed and appropriate laboratory tests (including CBC, plasma hemoglobin concentration, serum electrolytes) shall be obtained.

9.1.3 Test Dialysis Sessions

The assessment of the ability to successfully complete the session will be determined by the clinician and recorded on the Therapy Assessment Case Report Form (CRF). The actual treatment time will also be recorded. Adverse events will be recorded on an Adverse Event Case Report Form. Photos of the cannulation may be taken.

Additional performance measures include the following:

- Machine alarm rate (blood alarms only) during hemodialysis therapy, including false alarms and relationship of alarm to venous needle
- Changes to blood flow rate setting during therapy sessions and relationship to venous needle
- Venous, transmembrane, and/or arterial pressure measurements
- Patient survey including ratings for venous needle comfort and feelings of safety (V Needle only)
- Clinician survey, evaluating the following items:
 - use of the device according to the instructions for use (IFU)
 - ability to properly cannulate
 - ability to objectively see flashback
 - confirmation that the footplate is fully depressed (V Needle only)
 - feelings regarding patient risk (V Needle only)
- Achieved treatment time
- Achieved blood flow rate
- Ability to cannulate fistula
- Episodes of partial or complete needle dislodgment

In the event that the venous needle becomes 1) completely dislodged, or 2) partially dislodged and the venous pressure increases by more than 40 mm Hg (above last recorded venous pressure measurement) indicating some disruption of the fluid flow, the event should be recorded on the therapy assessment and AE CRFs and appropriate laboratory tests (including CBC, plasma hemoglobin concentration, serum electrolytes) shall be obtained.

Patients shall be monitored for symptoms of hemolysis; if hemolysis is suspected, an AE form should be completed and appropriate laboratory tests (including CBC, plasma hemoglobin concentration, serum electrolytes) shall be obtained.

9.1.4 Final Study Visit

7-10 days after the last study visit, subjects will be contacted by phone or will be interviewed at their usual hemodialysis session to ensure no additional AEs have occurred.

9.2 Safety and Other Assessments

9.2.1 Adverse Event Definitions

Adverse event forms will be filled out whenever an adverse event occurs within the reportable period. Definitions of the adverse event categories can be found below. Adverse events will be categorized according to a medical dictionary created by the sponsor and approved by the Data Safety Monitoring Board (DSMB) for reporting purposes.

Adverse Event (AE)	
Any untoward medical occurrence, unintended disease or injury, or untoward clinical signs (including abnormal laboratory findings) in participants, users, or other persons, whether or not related to the investigation medical device.
 
Note: Pain and/or bleeding that is to be expected due to hemodialysis during the intervention are not considered untoward events and should not be recorded as adverse events. Likewise, minimal bruising, pain, and/or bleeding in the days following the procedure shall not be considered untoward and not considered an AE. In contrast, any pain, bruising, or bleeding that is considered by the clinician to be unusual in magnitude or duration shall be considered an AE.

Adverse Device Effect (ADE)	
Adverse event related to the use of an investigational medical device.
 
Note: this definition includes adverse events resulting from insufficient or inadequate Instructions for Use, deployment, implantation, installation, or operation, or any malfunction of the investigational medical device. This definition includes any event resulting from use error or from intentional misuse of the investigational medical device.

Adverse Procedure Effect (APE)	Adverse event related to the therapeutic procedure for the investigational medical device.
Device Deficiencies (DD)	Any inadequacy in the identity, quality, durability, reliability, safety, or performance of an investigational device, including malfunction, use errors or inadequacy in information supplied by the manufacturer.
Serious Adverse Event (SAE)	
Any adverse event that led to any of the following:
 
• death• serious deterioration in the health of the participant that either resulted in:
▪ a life-threatening illness or injury,▪ a permanent impairment of a body structure or a body function,

	
 ▪ hospitalization or prolongation of patient hospitalization, ▪ medical or surgical intervention to prevent life-threatening illness or injury or permanent impairment to a body structure or a body function, ▪ chronic disease • fetal distress, fetal death or a congenital physical or mental impairment or birth defect 
Note: Planned hospitalization for a pre-existing condition, or a procedure required by the clinical investigational plan (CIP), without serious deterioration in health, is not considered a serious adverse event.

Serious Adverse Device Effect (SADE)	An adverse device effect that has resulted in any of the consequences characteristic of a serious adverse event.
Serious Adverse Procedure Effect (SAPE)	An adverse procedure effect that has resulted in any of the consequences characteristic of a serious adverse event.
Unanticipated Serious Adverse Device Effect (USADE)	
Serious adverse device effect which by its nature, incidence, severity, or outcome has not been identified in the current version of the risk analysis report
 
Note: Anticipated serious adverse device effect (ASADE) is an effect which by its nature, incidence, severity, or outcome has been identified in the risk analysis report.

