5.2 Scientific Rationale for Study Design

The study is designed to confirm the safety, performance, and usability of the V Needle, a new medical device. The device will be tested by comparing the ability to successfully complete hemodialysis sessions to commercially available devices as determined by a clinician.

Additionally, the rates of adverse events will be compared to rates measured using commercially available devices, providing a comparator with data collected under similar circumstances and in the same patient population.

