9.2.4 AE and DD information and Classification

The Investigator will classify each AE and DD according to the Adverse Event Form. If the AE is serious or the Investigator feels that the device contributed in any way to the AE, the Investigator must report the event to the Sponsor and the EC, if applicable, as per above. It is the Investigators responsibility to assess the intensity of, as well as determine the causality and potential relationship of the event to the study device or procedure. The Sponsor may ask for further clarification and information to support the AE classification. If sufficient questions arise, the Sponsor may ask the DSMB to adjudicate the classification. The Sponsor may assess the potential relationship to the device or procedure differently than the Investigator; in that case, both conclusions will be collected and reported, if applicable.

The following information will be collected for any event occurring during the course of this investigation:

- Date of event onset,

- In case of SAE, SADE, SAPE, USADE, DD that might have led to a SAE in other circumstances: classification of the event (death - life-threatening illness or injury - permanent impairment/chronic disease – hospitalization - medical or surgical intervention - fetal distress, fetal death or congenital physical or mental or birth defect)
- Description of the event
- Action / treatment / patient outcome
- Intensity of the event (mild, moderate, severe)
- Relationship to procedure (not related, possible, definite)
- Relationship to study device (not related, possible, definite)
- Event status (resolved, resolved with sequelae, ongoing, death)

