10.3.2 Safety Endpoint Analysis

The incidence rates of adverse events (including those listed under the primary and secondary safety endpoints) will be calculated as the number of events per number of treatments as well as tallied per subject. Adverse event rates will be summarized with 95% exact binomial confidence bounds for both the investigational and control groups.

The adverse events of each group will also all be stratified by their (1) seriousness, (2) severity, (3) relatedness to device, (4) relatedness to procedure, and (5) anticipated status.

Any events with onsets occurring between sessions will be associated with the group representing the device used at the last session.

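### Control-session rates of SADE and ADE (and, read literally, APE and SAPE) are zero by definition, so the control bounds planned in 10.3.2 carry no information for these measures

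*Combined protocol and SAP*

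**What the plan says.** All references are to the combined protocol and SAP.

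- **Definitions (9.2.1).** An ADE is "Adverse event related to the use of an investigational medical device", and an APE is "Adverse event related to the therapeutic procedure for the investigational medical device". SADE is "An adverse device effect that has resulted in any of the consequences characteristic of a serious adverse event" and SAPE is "An adverse procedure effect that has resulted in any of the consequences characteristic of a serious adverse event", so both inherit the restriction. An AE, by contrast, counts "whether or not related to the investigation medical device", and an SAE is any AE with a serious outcome.
- **Which device.** Section 1.7 identifies the study device as the V Needle. Sections 5.1 and 10.3.1 put three commercial-needle sessions first and six V Needle sessions after them.
- **Causality.** Section 9.2.11 has every AE graded against the study device or procedure. The data item in 9.2.4 is "Relationship to study device (not related, possible, definite". The procedure item beside it is not tied to either needle.
- **Analysis (10.3.2).** Rates are planned for events that include the primary safety endpoint: "Adverse event rates will be summarized with 95% exact binomial confidence bounds for both the investigational and control groups". Each group's events are also to be stratified by relatedness to device and to procedure.
- **Purpose (5.2).** The control sessions are there so that "the rates of adverse events will be compared to rates measured using commercially available devices".

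**The concern.** Section 3.3.1 lists infection, blood loss, infiltration and hemolysis among the risks of all AV fistula sets, so the commercial needle can cause the same harms as the V Needle. Under the definitions, an injury caused by the needle is a device effect in a V Needle session but has no corresponding category in a control session.

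SADE is the only primary safety measure. A control SADE or ADE row printed with an exact confidence interval would look like an estimate of the commercial needle's rate, but it would describe a count that cannot vary. A reader who sets the two rows side by side would charge the V Needle with harms common to both needles.

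**Working it through.** **Inputs.** Session counts are from 10.3.1 (18 subjects; 108 test and 54 control sessions) and 5.3 (15 subjects, nine treatments each). The interval method is the exact binomial of 10.3.2. The plan gives no event rate for any safety measure, so the rates in step 3 are assumptions, shown as a range.

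The session counts reproduce: 18 × 6 = 108 and 18 × 3 = 54; with 15 subjects, 15 × 3 = 45 control sessions. The plan states no figure for the safety comparison. Its powered figure of 87 test sessions is for session success and does not bear on this point.

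**Step 1: which measures can be non-zero in a control session, in the planned order?**

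| Measure | Tied by 9.2.1 to | Possible in a control session? |
|---|---|---|
| AE | nothing | yes |
| SAE | nothing (serious AE) | yes |
| ADE | investigational device | no |
| SADE (primary) | investigational device | no |
| APE | procedure for the investigational device | no if read literally; the procedure item in 9.2.4 is unqualified |
| SAPE | as APE | as APE |

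The endpoint lists in 4.1 and 4.2 speak of device and procedure events, while 9.2.1 defines device and procedure effects. I take them to be the same.

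**Step 2: what 10.3.2 would print.** For 0 events in n sessions the exact 95% interval runs from 0 to 1 − 0.025^(1/n).

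- Control, n = 54: 1 − 0.025^(1/54) = 6.6%.
- Control, n = 45: 1 − 0.025^(1/45) = 7.9%.
- V Needle, n = 108, if no event occurs: 1 − 0.025^(1/108) = 3.4%.

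A table of 0/108 (0% to 3.4%) beside 0/54 (0% to 6.6%) would look like two estimates of the same kind. Only the first could have come out otherwise.

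**Step 3: size of the tilt.** Let p be the true per-session rate of needle-related events with the V Needle and r the rate with the commercial needle. The true difference is p − r. The tabulated difference has expectation p − 0 = p. The distortion is therefore p − (p − r) = r. With equal rates assumed (p = r):

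| Assumed rate | Expected V Needle events (× 108) | Expected control events (× 54) | Control events tabulated |
|---|---|---|---|
| 1% | 1.1 | 0.5 | 0 |
| 2% | 2.2 | 1.1 | 0 |
| 5% | 5.4 | 2.7 | 0 |

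**The case against.** A reader might infer that the own-control safety comparison fails altogether. The documents do not support that. The comparison described in 1.1, 1.8 and 5.2 is of adverse event rates. AE and SAE are defined without regard to the device, and 10.3.2 assigns events arising between sessions to the needle last used. A commercial-needle infiltration that qualifies as an AE therefore enters the control AE rate, and the SAE rate if serious. This part of the objection stands in full.

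Nor does a safety decision rest on the affected row. Section 10.3.2 is descriptive, with no safety hypothesis, margin, test or success criterion. The stopping provision in 5.3 counts SADEs in the study device period, which fits SADE as a V Needle quantity. The powered analysis of session success is untouched, and the tilt could not produce a false claim in the V Needle's favour. This stands too, and it limits the severity.

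It is also tempting to say that every commercial-needle injury must be coded as unrelated and that four of the six measures are certain zeros. That goes too far. Section 9.2.2 asks for relationship to the medical device without qualification, 9.2.4 has the unqualified procedure item, and 10.3.2 stratifies both groups by relatedness. The AE form itself is not in the documents. Sites could therefore record some control events as related, most plausibly to procedure. This softens the point for APE and SAPE but does not rescue the control row: it would be either a forced zero or a mixture of coding habits.

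Finally, true SADEs may be so rare that a zero is expected anyway. At an assumed 0.5% per session, 54 × 0.005 = 0.27 control events are expected, and 0.995^54 = 76% of such trials would show none even under symmetric definitions. That is fair for SADE. It applies less to ADE, where commoner events count, and it does not turn a structural zero into an estimate.

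**Conclusion.** The plan is wrong as written on this point, with moderate severity. Following 9.2.1 literally and in the planned session order, control SADE and ADE are structurally zero, and the bounds that 10.3.2 would attach (0% to 6.6% for 54 sessions, 0% to 7.9% for 45) say nothing about the commercial needle. The same holds for APE and SAPE on the literal wording, with the ambiguity noted. No other section supplies a device-relatedness definition for the control needle.

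The tilt against the V Needle equals the true commercial-needle rate, which the documents do not give; the 1% to 5% range is illustrative only. The structural zero also assumes that control sessions precede test sessions. If a site reverses the order, the last-session rule could assign a late V Needle effect to the control group.

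AE and SAE remain a usable own-control comparison. They cannot, however, separate needle-related harm from everything else that happens to dialysis patients.

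**What to change.** - **9.2.4 and the AE form:** add an item for relationship to the venous needle in use at the session (V Needle or commercial needle), graded not related, possible or definite, and completed in both periods. Sections 9.1.2 and 9.1.3 already attribute alarms and blood-flow changes to the venous needle in this neutral way.
- **9.2.4:** state that the procedure item refers to the cannulation and dialysis procedure in both periods.
- **10.3.2:** compare needle-related, serious needle-related, AE and SAE rates between groups. Report ADE and SADE for V Needle sessions only.
- **9.2.1:** leave the regulatory definitions unchanged.

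The cost is one form field and wording in two sections, with no new visits or procedures. It should be in place before a subject's control sessions. These come first, and attribution not captured then would have to be reconstructed later with outcomes known.
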